### 3.3.7 Sample Size

#### Substudy 1

Across all parts of the study up to a total of 165 participants may be enrolled and treated with AZD8853 (145 participants if 20 participants from Part B are included in Part C).

##### 3.3.7.1 Dose escalation: mTPI-2

###### Part A: Substudy 1

The Modified Toxicity Probability Interval-2 (mTPI-2) employs a simple beta-binomial Bayesian model (Guo et al 2017). The posterior density of the toxicity probability is divided into multiple intervals with equal length. These intervals are categorized as underdosing (below), proper dosing (equivalent), and overdosing (above) in terms of target toxicity. The underdosing interval corresponds to a dose escalation, overdosing corresponds to a dose de-escalation, and proper dosing corresponds to staying at the current dose. The design for the dose-escalation phase of the study uses a target Dose Limiting Toxicity (DLT) rate of **[REDACTED]**% and an equivalence interval **[REDACTED]** for dose-escalation/de-escalation decisions as well as MTD determination. A dose level is considered unsafe, with no additional participants enrolled at that dose level, if it has an estimated 95% or more probability of exceeding the target DLT rate of **[REDACTED]**% (i.e.,  $P [DLT > [REDACTED]\% | \text{data}] \geq 95\%$ ).

For specific dose escalation rules, refer to CSP Section 10.6.6.1.3.

For dose escalation (Part A) cohorts of at least 3 and up to 9 evaluable participants are required for each dose cohort (unless unacceptable toxicity is seen before 3 evaluable participants). The total number of participants will depend on the number of non-evaluable participants and the number of dose escalations necessary in order to declare MTD/RP2D. More patients may also need to be enrolled to a dose level if toxicity is observed. It is anticipated that approximately up to 5 dose-escalation cohorts of up to 9 evaluable participants may be included resulting in an overall total of up to approximately 45 participants.

The dosing cohorts are grouped depending on the starting dose they are planned. The starting dose for this study is 300 mg with the maximum dose set at 3000 mg.

### 3.3.7.2 Dose Expansion

#### Part B: Substudy 1

[figure not shown]
In the PD/MoA expansions (Part B1 and B2) up to approximately 10 participants may be enrolled in each of 2 dose levels and 2 indications (Non-Small-Cell Lung Cancer [NSCLC] and Microsatellite Stable-Colorectal Cancer [MSS-CRC]) for a total of approximately 40 participants. It is thought that approximately 20 participants enrolled in part B of the study will participate in CD8+ PET imaging.

#### Part C: Sub Study 1

At least 40 participants will be enrolled in each efficacy expansion (part C1 and C2) for a total of 80 participants. This will be an additional 30 participants per expansion since 10 relevant participants may be included from the associated PD/MoA expansion. The sample size has been determined to provide sufficient precision for the estimation of ORR. With 40 participants in each expansion, CCI

CI. CIs are constructed around the response rates observed in each population using the Clopper-Pearson method (Clopper and Pearson 1934) to enable decisions to be made about the likely success of future studies in each of the populations. For example:

CCI

## 4 STATISTICAL ANALYSIS

This section provides information on definitions, derivation, and analysis/data presentation per domain.

### 4.1 Study Population

The domain study population covers participant disposition, analysis sets, protocol deviations, demographics, baseline characteristics medical history, prior and concomitant medication.

#### 4.1.1 Participant Disposition and Completion Status

##### 4.1.1.1 Definitions and Derivations

Participants screened is defined as informed consent received. Further details are provided in CSP Section 10.5. Participants are followed until either death, lost to follow up or withdrawal of consent or end of study. Participants who permanently discontinue from study intervention remain in the study follow up until death or withdrawal of consent. Further information is defined in CSP section 7.1.

Completion of study is defined in CSP Section 4.4 as 18 months after the last enrolled participant received his/her first dose of IP or when the sponsor stops the study, whichever occurs first.

##### 4.1.1.2 Presentation

Participant disposition including screen failures and reason for screen failure are summarised and listed based on all participants screened (i.e., informed consent received) by the current relevant tables, figures, listings (TFL) standards.

The number and percentage of participants for the following are summarised if applicable:

- Participants screened.
- Screen failures.
- Participants assigned to treatment.
- Participants assigned to treatment, but who were not treated.
- Participants who started treatment.
- Participants ongoing treatment at DCO.
- Participants who discontinued treatment, and reason if applicable.

- Participants ongoing study at DCO.
- Participants who withdrew from study and reason if applicable.
- Participants who completed study

Summaries on disposition due to global/country situation are added to the disposition table if applicable. The number and percentage of participants for the following summaries are added if applicable:

- Participants who discontinued treatment due to global/country situation.
- Participants who withdrew from study due to global/country situation.

Data for each Substudy will be presented as per Section [3.3.](#)

#### **4.1.2 Analysis Sets**

##### **4.1.2.1 Definitions and Derivations**

For the definitions of each analysis set, refer to section [3.2.](#)

##### **4.1.2.2 Presentation**

Data for each Substudy will be presented as per Section [3.3.](#)

Any exclusions from analysis sets are listed.

#### **4.1.3 Protocol Deviations**

##### **4.1.3.1 Definitions and Derivations**

The examples of the categories are shown in Section [3.3.5.](#)

##### **4.1.3.2 Presentation**

The incidence of IPDs is summarised by deviation categories on the safety analysis set by deviation category. The number and percentage of participants in the following categories are summarised:

- Number of participants with at least 1 IPD.
- Number of participants with at least 1 COVID-19 related IPD.
- Number of participants with at least 1 IPD, excluding COVID-19 related IPDs.

For each summary above, the number and percentage of participants with each IPD is also presented.

A listing is provided with the important protocol deviation details. IPDs resulting from coronavirus disease 2019 (COVID-19) circumstances are also included, if any.

Data for each Substudy will be presented as per Section [3.3.](#)

#### **4.1.4 Demographics**

##### **4.1.4.1 Definitions and Derivations**

Age (years) is grouped accordingly in the following categories: < 65,  $\geq$  65 years. Each race category counts participants who selected only that category.

Number of nicotine pack years is derived as the following:

If nicotine substance use is collected daily:

Number of Nicotine pack years=

Number of nicotine packs per day \* Number of years the patient has smoked

If nicotine substance use is collected weekly:

Number of Nicotine pack years=

( Number of nicotine packs per week /7 ) \* Number of years the patient has smoked

##### **4.1.4.2 Presentation**

Demographics for Substudy 1 are summarised and listed based on the safety analysis set as defined by the current relevant TFL standards.

The following are summarised:

- Age (years)
- Age group
- Sex
- Race
- Ethnicity

Participant recruitment per country and site is summarised by the safety population.

Participant's substance (nicotine) use, frequency of substance use and number of pack year, is also summarised in a separate table for the safety population.

If data allows (i.e., there are more than 5 participants with this data), demographic characteristics in participants with confirmed COVID-19 infection are summarised, otherwise only listings for these participants are provided.

Data for each Substudy will be presented as per Section [3.3.](#)

#### **4.1.5 Baseline Characteristics**

##### **4.1.5.1 Definitions and Derivations**

Body mass index (BMI) is calculated as:

$$\text{BMI}(\text{kg}/\text{m}^2) = \frac{\text{weight}(\text{kg})}{(\text{height}(\text{m}))^2}$$

##### **4.1.5.2 Presentation**

Baseline characteristics are listed and summarised for the safety analysis set.

The following are summarised:

- height (cm)
- weight (kg)
- BMI (kg/m^2)

Data for each Substudy will be presented as per Section [3.3.](#)

#### **4.1.6 Disease Characteristics**

##### **4.1.6.1 Definitions and Derivations**

Time from original diagnosis to first dose of IP (in months) is calculated as:

$$\text{Time from original diagnosis (months)} = \frac{(\text{Date of first dose of IP}-\text{Date of original diagnosis}+1)}{(\frac{365.25}{12})}$$

Time since last cancer therapy to first dose of IP (in days) is calculated as:

Time since last therapy

$$(\text{days}) = (\text{Date of first dose of IP}-\text{Stop date of last cancer therapy}+1)$$

Time since diagnosis of metastatic disease to first dose of IP (in months) is calculated as:

$$\text{Time since diagnosis of metastatic disease (months)} = \frac{(\text{Date of first dose of IP}-\text{date of first diagnosis of metastatic disease}+1)}{(\frac{365.25}{12})}$$

Time since most recent date of progression to date of first dose of IP (in days) is calculated as:

Time since most recent date of progression  
(days)= (Date of first dose of IP-date of most recent progression +1)

#### **4.1.6.2 Presentation**

Disease characteristics at baseline are summarised and listed based on the safety analysis set as defined by the current relevant TFL standards.

Summaries are to be produced that present the number and percentage of participants on their:

- Histology type at diagnosis
- Tumour grade at diagnosis
- American Joint Committee on Cancer (AJCC) stage at diagnosis
- Eastern Cooperative Oncology Group Performance Status (ECOG PS)
- Primary tumour location at diagnosis
- Local/metastatic sites at study entry
- Tumour Node and Metastases (TNM) classification for primary tumour at time of diagnosis and study entry
- **CCI** [REDACTED]
- Location of target lesions at baseline

Summary statistics are presented for participants' time from original diagnosis to first dose (months), time since last cancer therapy (days), time since diagnosis of metastatic disease (months), time since most recent progression (days), number of target Lesions (NTLs), sum of diameter of Target Lesions (TLs) and number of metastatic sites.

Data for each Substudy will be presented as per Section [3.3](#).

#### **4.1.7 Medical History and Concomitant Disease**

##### **4.1.7.1 Definitions and Derivations**

Medical history and relevant surgical history, including both resolved and ongoing conditions at the time of study entry, are summarized by the primary system organ class (SOC) and

preferred term (PT) in accordance with the latest medical dictionary for regulatory activities (MedDRA) at the time of DBL/analysis.

### **Previous Immunotherapy**

The time from most recent immunotherapy to first dose of IP is calculated as:

Time since most recent immunotherapy treatment

(Days) = (Date of first dose of IP-end date of last immunotherapy treatment + 1)

The duration of the last immunotherapy prior to study entry is calculated as:

Length of last immunotherapy treatment (days) =

(End date of last immunotherapy treatment - Start date of first immunotherapy treatment + 1)

Where last immunotherapy is defined as the last immunotherapy administrated prior to study drug.

The length of all prior immunotherapy prior to study entry is calculated as:

Length of all immunotherapy treatments (days) =  $\sum_{i=1}^N (End\ Date\ of\ immunotherapy\ treatment_i - Start\ date\ of\ immunotherapy\ treatment_i + 1)$

Where  $N$  total number of immunotherapies received by the patient before first dose of IP

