10.5.1 Substudy 1 Inclusion Criteria

In addition to the master study inclusion criteria listed in Section 5.1, participants are eligible to be included in this Substudy only if the further Substudy 1 criteria below also apply:

- 1 Histologically or cytologically documented unresectable, locally advanced (Stage III) or metastatic (Stage IV) NSCLC, metastatic (Stage IV) MSS-CRC or metastatic (Stage IV) UC.
- 2 Participants must meet all of the tumour-specific criteria below, with documented progression from previous therapy at study entry. Interval progression between 2 lines of therapy defines separate lines of therapy. Both standard and investigational treatments will count as lines of therapy when determining eligibility.
 - (a) Participants with NSCLC must:
 - i. Have received at least one prior line of systemic therapy in the advanced/metastatic setting.
 - ii. Have received at least one prior line of therapy which contained an anti-PD-1/PD-L1 agent, with or without platinum-based chemotherapy.
 - iii. Have documented test results for:
 - Sensitizing EGFR mutations and ALK fusions/rearrangements
 - Other genomic alterations which are part of a local standard of care and for which a locally approved standard of care targeted therapy exists (such as ROS proto-oncogene 1 [ROS1] fusions/rearrangements, neurotrophic receptor tyrosine kinase (NTRK) fusions, RET fusions/rearrangements, MET exon 14 skipping mutations, BRAF V600E mutation, etc.).
 - iv. Have received targeted therapy according to the identified genomic alteration.

 Targeted therapy is not mandatory if it is not in the local standard of care, or if it is refused by the participant or contraindicated.
 - v. For Parts B and C: PD/MoA and Efficacy Expansions:

 No sensitizing EGFR mutations or ALK fusions/rearrangements (documented test result is mandatory).
 - (b) Participants with MSS-CRC:
 - i. Must have documented MSS by local testing (genetic analysis or immunohistochemistry).
 - ii. Must have received at least 2 prior lines of systemic therapy for advanced/metastatic disease.
 - Prior systemic therapies must include fluoropyrimidines, irinotecan and oxaliplatin, unless refused or contraindicated. Participants may or may not have received a vascular endothelial growth factor (VEGF) agent (eg, bevacizumab), a BRAF inhibitor and an EGFR therapy (eg, cetuximab or panitumumab), according to local standard or care.

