10.5.2 Substudy 1 Exclusion Criteria

In addition to the master study exclusion criteria listed in Section 5.2, participants are excluded from this Substudy if any of the further Substudy 1 criteria below also apply:

- 1. Participants who have received prior immunotherapy with anti-PD-1, anti-PD-L1, or anti-CTLA-4:
 - a) Must not have experienced a toxicity that led to permanent discontinuation of prior immunotherapy.
 - b) All AEs while receiving prior immunotherapy must have completely resolved or resolved to baseline prior to screening for this study.
 - c) Must not have experienced a ≥ Grade 3 imAE or a neurologic or ocular imAE of any grade while receiving prior immunotherapy. Note: Participants with an endocrine AE of ≤ Grade 2 are permitted to enrol if they are stably maintained on appropriate replacement therapy and are asymptomatic.

- d) Must not have required the use of additional immunosuppression other than corticosteroids for the management of an AE, not have experienced recurrence of an AE if re-challenged, and not currently require maintenance doses of > 10 mg prednisone or equivalent per day.
- 2. Participants with spinal cord compression or history of leptomeningeal carcinomatosis.
- 3. Participants with brain metastases unless treated, asymptomatic, stable, and not requiring continuous corticosteroids at a dose of > 10 mg prednisone/day or equivalent for at least 4 weeks prior to the start of the study.
- 4. Exclusion criteria for participation in the study include:
 a) CCI
 b) CCI

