### **Previous immunotherapy:**

Summary statistics are presented for time from the last immunotherapy treatment to first IP dose (days) and duration of last prior immunotherapy treatment (days). This information will also be presented for immediate immunotherapy, including only patients for whom the last therapy they had prior to study IP was immunotherapy. Summary statistics are presented for the length all immunotherapy treatments.

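### The SAP computes the length of the last prior immunotherapy from the start of the first one, so the value is too long whenever the last began after the first

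*SAP*

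**What the plan says.** SAP section 4.1.7.1, under Previous Immunotherapy, defines three quantities.

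- **Time since the most recent immunotherapy:** date of first dose of study drug minus end date of the last immunotherapy, plus 1.
- **Length of the last immunotherapy:** introduced by "The duration of the last immunotherapy prior to study entry is calculated as" and given as "End date of last immunotherapy treatment - Start date of first immunotherapy treatment + 1". The line below it reads "Where last immunotherapy is defined as the last immunotherapy administrated prior to study drug".
- **Length of all immunotherapies:** introduced by "The length of all prior immunotherapy prior to study entry is calculated as" and given as a sum over i = 1 to N of each therapy's own end date minus its own start date, plus 1. N is the number of immunotherapies received before study drug.

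Section 4.1.7.2 then promises summary statistics for all three. For the first two it adds "This information will also be presented for immediate immunotherapy", meaning a repeat in participants whose last therapy before study drug was an immunotherapy.

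**The concern.** The lead-in sentence, the label and the definition below the formula all describe one therapy, the last one. The formula uses that therapy's end date with a different therapy's start date. For a participant with sequential immunotherapies, the result takes in the earlier courses and the time off treatment between them.

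The Protocol leaves room for such participants. For NSCLC, section 10.5.1 sets a minimum and no maximum: "Have received at least one prior line of therapy which contained an" anti-PD-1/PD-L1 agent. Section 10.5.2 requires that participants with prior immunotherapy must "not have experienced recurrence of an AE if re-challenged", so repeat exposure is foreseen. The SAP's sum over N therapies also expects N to exceed 1.

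At stake is a baseline table in which one row is inflated and can contradict the row for total immunotherapy length.

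**Working it through.** The plan gives no worked figure to reproduce, and the documents contain no participant dates. All dates and course lengths below are assumptions chosen to show how the formula behaves. S and E are the start and end dates of a therapy. Where therapies overlap, the last is taken as the one that ended last.

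**Formulas**

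- SAP length of last = E(last) − S(first) + 1
- Length that matches the label = E(last) − S(last) + 1
- SAP length of all = sum of (E_i − S_i + 1)

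**General result for two sequential courses**

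- SAP length of last minus true length of last = S2 − S1. This is zero only if both began on the same day.
- SAP length of last minus SAP length of all = (E2 − S1 + 1) − (E1 − S1 + 1) − (E2 − S2 + 1) = S2 − E1 − 1. This is the number of treatment-free days between the courses, so one such day is enough to make last longer than all.

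**Worked example (assumed dates)**

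- Course 1, 1 January to 30 June 2020: 31 + 29 + 31 + 30 + 31 + 30 = 182 days.
- Course 2, 1 January to 31 March 2021: 31 + 28 + 31 = 90 days.
- SAP length of last, 1 January 2020 to 31 March 2021: 366 + 90 = 456 days.
- True length of last: 90 days. SAP length of all: 182 + 90 = 272 days.
- Check: 456 − 272 = 184, the number of days from 1 July to 31 December 2020.

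**Other assumed patterns (days)**

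| Pattern | SAP length of last | True length of last | SAP length of all |
|---|---|---|---|
| One therapy, 180 days | 180 | 180 | 180 |
| 180 then 90 days, contiguous | 270 | 90 | 270 |
| 180 then 90 days, one treatment-free day | 271 | 90 | 270 |
| 180 then 90 days, one-year gap | 635 | 90 | 270 |
| Two of 180 days, overlapping, different starts | 270 | 180 | 360 |
| 90 and 180 days, same start date | 180 | 180 | 270 |

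The formula is right in the first and last rows and too long in the other four. It exceeds the total only in the two rows with a treatment-free interval.

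**Is it corrected elsewhere?** No. The SAP amendment history records corrections to neighbouring descriptive derivations (the units of time since last cancer therapy and of time since most recent progression) but does not mention this formula. No other section restates it.

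**The case against.** **The intent is obvious.** The label, lead-in, definition and output name all point to the last therapy, and a careful programmer might correct the slip unprompted. That is fair, but the formula is the instruction, and coded literally it gives the wrong value.

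**A charitable reading exists.** The subtracted date could mean the first administration within the last therapy. The same subsection rules this out: its sum gives each numbered treatment its own start and end, so a treatment there is a whole therapy.

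**Duration is reported elsewhere.** The Previous Cancer Therapy part of section 4.1.7.2 separately summarises treatment duration and time since last dose for previous treatments, and the other two immunotherapy quantities are defined correctly. This limits the damage but does not repair the affected row.

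**Stronger readings are tempting.** A reader might infer three things that the documents do not support.

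- *That the value is wrong for everyone with two or more immunotherapies.* It is correct when all of them began on the same day, as with a combination recorded as separate entries.
- *That the variable is used to judge resistance to prior immunotherapy or to interpret response.* No section says so. The derivations of ORR, DCR, DoR, PFS and OS do not take it as an input. SAP sections 4.2.2.6 and 4.2.3.6 mark subgroup analyses of ORR and best overall response as not applicable, and the DoR and OS sections refer back to 4.2.2.6.
- *That most of the NSCLC rows will be wrong because prior anti-PD-1/PD-L1 therapy is required.* The requirement makes prior exposure universal in that group. It does not show that sequential courses are common, and a single course is computed correctly. UC participants may qualify on platinum alone, and MSS-CRC has no immunotherapy requirement.

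**Conclusion.** The derivation is wrong as written. It overstates the length of the last immunotherapy for any participant whose last one began after the first. For two courses the error is the interval between their start dates: 366 days in the worked example (456 − 90). With a treatment-free interval between sequential courses, the value also exceeds the SAP's own total.

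The consequence is small. It is confined to one descriptive summary of prior therapy and its repeat for immediate immunotherapy. No primary or secondary endpoint is touched. The sizes shown rest on assumed dates, and the share of participants affected cannot be estimated from the documents.

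**What to change.** In the SAP section 4.1.7.1 formula for the length of the last immunotherapy, change the subtracted date from the start of the first immunotherapy to the start of the last, giving E(last) − S(last) + 1. Check any existing program for this variable and for the immediate-immunotherapy repeat against the corrected formula.

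The cost is one word in the SAP plus the program check. The total-length sum already uses each therapy's own start and end dates, so no new data are needed, and nothing in the design changes.
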